8.1.5.4 Safety

Adverse events, incidents and expected side effects of the medical device will be reported in the CRF at each visit/telephone call.

8.1.6 Arrangements for the monitoring maintenance and calibration of equipment used for genomic analysis

Annual maintenance by the manufacturer is performed on the Freedom EVO 150 (Tecan) and pipetting volumes are regularly controlled. The ViiA 7 Real-Time PCR System (ThermoFisher Scientific) is monthly controlled by Vaiomer staff and annually calibrated by the manufacturer. All handling, measurement and safety equipment (e.g. pipettes, scale, Captair Biocap PCR Workstations, spectrophotometers, safety and fume hoods) is annually controlled by specialized providers.

8.1.7 Any procedures for the replacement of subjects

No replacement of subjects is planned.

8.1.8 Investigation sites: number, location

The clinical investigation will be undertaken in 1 site in France. The principal investigator, [name] is Otorhinolaryngologist and familiar with study procedures.

8.1.9 Definition of the completion of the study

This is defined as the date of last patient last visit (LPLV).

8.2 Investigational device and comparator

The investigational device which is Healsea® Chronic (nasal spray; 150 mL presentation) is a CE marked Medical Device. As this is an interventional study, the device will be provided to the patient. No specific labelling is required as the device will be used within its intended use in this post-market clinical investigation.

No comparator is used in this study.

8.3 Subjects

The target population is adult patients patients over 18 years diagnosed with CRS according to EPOS criteria [1]. According to these criteria, chronic rhinosinusitis (with or without nasal polyps) in adults is defined as presence of two or more symptoms one of which should be either nasal blockage/obstruction/ congestion or nasal discharge (anterior/posterior nasal drip), \pm Facial pain/pressure \pm reduction or loss of smell, lasting for 12 weeks or longer.

The subjects will be recruited by the site among outpatients coming for routine consultation because of CRS.

8.3.1 Eligibility criteria

8.3.1.1 *Inclusion criteria*

In order to be eligible to participate in this study, an individual must meet all of the following criteria:

1. Male or female, aged $\geq 18 - \leq 70$ years
2. Provision of signed and dated informed consent form
3. Stated willingness to comply with all study procedures and availability for the duration of the study
4. Diagnosed with CRS based on the diagnostic criteria of the EPOS guideline
5. Registered with a social security scheme or covered by such a regime

8.3.1.2 *Non-inclusion Criteria*

An individual who meets any of the following criteria will be excluded from participation in this study:

1. Antibiotics or oral corticosteroids intake in the month prior to the study
2. Endoscopic sinus surgery in the 6 past months
3. Cystic fibrosis
4. Wegener's granulomatosis
5. Immunodeficiency
6. Defective access to the middle meatus
7. Lidocaine allergy
8. Known hypersensitivity/allergy to any component of the test device
9. Pregnant/Lactating female or absence of efficient contraception
10. Under tutorship or guardianship

8.3.2 Criteria and procedures for subject withdrawal or lost to follow-up

8.3.2.1 *Withdrawal Criteria and procedures*

The reasons for a subject's premature withdrawal from the study may be the following:

- A subject can withdraw his/her consent from the study for any reason at any time but he/she must inform the investigator. In all cases, whenever possible, the investigator should attempt to contact the patient as soon as possible for a final assessment in order to:
 - Obtain the reason(s) for withdrawal and report it/them in the Case Report Form,
 - Evaluate the patient's clinical condition,
 - If necessary, take appropriate therapeutic measures: management of an adverse effect or concomitant disease, prescription of another treatment.

An investigator may discontinue or withdraw a participant from the study for the following reasons:

- Significant study product non-compliance,
- If any clinical adverse event (AE)/incident, laboratory abnormality, or other medical condition or situation occurs such that continued participation in the study would not be in the best interest of the participant,

- If the participant meets an exclusion criterion (either newly developed or not previously recognized) that precludes further study participation. In the context of COVID-19 pandemic, the diagnosis of COVID-19 during the study will justify the withdrawal of the patient from the study.

A premature end of study visit will be scheduled. Available data will be retained for the safety/efficacy analysis.

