4.9 Reference to the IFU

The IFU of Healsea® Chronic is provided in Appendix A.

5. Justification for the design of the clinical investigation

Chronic rhinosinusitis (CRS) is an inflammation of the nose and paranasal sinuses and is characterized by two or more symptoms, one of which should be either nasal blockage/obstruction/congestion or nasal discharge (anterior/posterior nasal drip), lasting for 12 weeks or longer. In addition, facial pain or pressure and a reduction in the sense of smell can occur [1]. The condition can occur with or without nasal polyps.

The overall prevalence of symptom-based CRS in the population has been found to be between 5% and 12% [1].

The physiopathology of CRS is poorly understood with multiple environmental, host and microbial factors being implicated. Putative pathological factors include changes in the microbiota, imbalance of the local or systemic immune system, allergens, toxins and genetic predisposition [2].

A dysbiosis mechanism has been proposed as modulating inflammation in diseased sinuses. This hypothesis suggests that externally influenced changes in the nasal microbiome can result in dysbiosis, i.e. a shift from a “normal” or “healthy” microbial community structure and that this shift may be responsible for the initiation or maintenance of CRS. For example, the disruption of the commensal biofilm during a viral upper respiratory tract infection can create a niche for pathogenic species to grow [3]. Despite many contradictory statements in the different studies some common trends emerge. Less diversity in the microbial community rather than an increased overall bacterial load seems to characterize CRS compared to the healthy state with no consensus about specific genera indicative of disease [4], [5], [6]. However, anaerobes and *S. aureus* are found to be significantly more prevalent and abundant in CRS versus healthy controls [4]. Bacterial biofilm is detected on the sinus mucosa in up to 80% of CRS patients and its presence does not imply that it is causing mucosal inflammation. However, in the context of CRS, there are several possible mechanisms by which biofilms may be pro-inflammatory including the release of planktonic organisms and the release of superantigens, which can cause ciliary dysfunction and inhibition of ciliary clearance. Bacterial biofilms are likely a key modulator of the refractory nature of CRS [7].

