Appendix B: SNOT-22**Sino-Nasal Outcome Test-22 Questionnaire v4**

Below you will find a list of symptoms and social/emotional consequences of your nasal disorder. We would like to know more about these problems and would appreciate you answering the following question to the best of your ability. There are no right or wrong answers, and only you can provide us with this information. Please rate your problems, as they have been over the past two weeks. Thank you for your participation.

Considering how severe the problem is when you experience it and how frequently it happens, please rate each item below on how 'bad' it is by circling the number that corresponds with how you feel using this scale →

	No problem	Very mild problem	Mild or slight problem	Moderate problem	Severe problem	Problem as bad as it can be
1. Need to blow nose	0	1	2	3	4	5
2. Sneezing	0	1	2	3	4	5
3. Runny nose	0	1	2	3	4	5
4. Cough	0	1	2	3	4	5
5. Post nasal discharge (dripping at the back of your nose)	0	1	2	3	4	5
6. Thick nasal discharge	0	1	2	3	4	5
7. Ear fullness	0	1	2	3	4	5
8. Dizziness	0	1	2	3	4	5
9. Ear pain/pressure	0	1	2	3	4	5
10. Facial pain/pressure	0	1	2	3	4	5
11. Difficulty falling asleep	0	1	2	3	4	5
12. Waking up at night	0	1	2	3	4	5
13. Lack of a good night's sleep	0	1	2	3	4	5
14. Waking up tired	0	1	2	3	4	5
15. Fatigue during the day	0	1	2	3	4	5
16. Reduced productivity	0	1	2	3	4	5
17. Reduced concentration	0	1	2	3	4	5
18. Frustrated/restless/irritable	0	1	2	3	4	5
19. Sad	0	1	2	3	4	5
20. Embarrassed	0	1	2	3	4	5
21. Sense of taste/smell	0	1	2	3	4	5
22. Blockage/congestion of nose	0	1	2	3	4	5

TOTAL: — — — — —

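### No eligibility criterion covers COVID-19 or acute respiratory infection at V1, so in a study without controls recovery from one cannot be told apart from change on the device

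*Protocol*

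**What the plan says.** **Withdrawal.** Protocol 8.3.2.1 opens its list of investigator-initiated reasons with "An investigator may discontinue or withdraw a participant from the study for the following reasons". One reason reads "If the participant meets an exclusion criterion (either newly developed or not previously recognized) that precludes further study participation", and the same bullet continues: "In the context of COVID-19 pandemic, the diagnosis of COVID-19 during the study will justify the withdrawal of the patient from the study". The section then provides for a premature end-of-study visit and keeps the available data for the safety and efficacy analyses.

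**Eligibility.** Protocol 8.3.1.2 is introduced by "An individual who meets any of the following criteria will be excluded from participation in this study" and has ten items, repeated in the synopsis. None concerns COVID-19, a cold or another acute respiratory infection. The nearest is criterion 1: "Antibiotics or oral corticosteroids intake in the month prior to the study".

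**Rationale.** Protocol section 5 and the synopsis say that "the disruption of the commensal biofilm during a viral upper respiratory tract infection can create a niche for pathogenic species to grow".

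**Design and endpoints.** Section 8.1.1 considers a control group unnecessary. Section 8.1.2 marks measures against bias as not applicable, and 8.4.5 anticipates no factor that could compromise the outcome. Section 8.1.3 reads the before/after comparison as the impact of the device on the microbiome. SNOT-22 is completed at V1 and at V2 (Day 30 ± 5), with the instruction in Appendix B: "Please rate your problems, as they have been over the past two weeks". The sample is 20 patients (8.3.6) and no replacement is planned (8.1.7).

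**The concern.** The protocol treats COVID-19 during follow-up as important enough to justify withdrawal, and ties this to an exclusion criterion that the eligibility list does not contain. It also names viral respiratory infection as something that changes which organisms grow in the nose. It nevertheless does not ask whether such an infection is present, or recent, when the baseline swab is taken. A site that applies 8.3.1.2 as written can enrol a CRS patient with a cold or very recent COVID-19, provided no antibiotic or oral corticosteroid was taken in the past month.

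If that infection has cleared about 30 days later, the V1 swab shows a temporarily disturbed community and the V1 SNOT-22 includes the infection through its two-week recall. Both would move by V2 without any device effect, and no control arm shows how far. Protocol 6.6 says that an observed improvement of the microbiota could justify larger studies, so a mistaken signal would have consequences even though the study is exploratory.

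**Working it through.** The plan has no figure to reproduce: the sample size is called arbitrary and no effect size, SD or infection rate is given. The check is a reading of the text followed by an illustration on stated assumptions.

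**1. Can a patient infected at V1 enter and stay in?**
- Inclusion criterion 4 requires CRS by EPOS. Section 8.3 describes this as symptoms for 12 weeks or longer, which does not rule out an acute infection on top.
- Criterion 1 stops only patients who were treated with antibiotics or oral corticosteroids.
- Major deviations (protocol section 13, SAP 7.2) are eligibility breaches, treatment non-compliance, missing swabs and forbidden medication. An infection at V1 is none of these.
- The FAS (SAP section 5) needs device use and one post-baseline SNOT-22. The committee may remove patients who fail major entry criteria, but here no entry criterion is failed.
- The SAP plans no sensitivity analysis on infection. The primary analysis and its population are left to a separate document (SAP 10.1), which is not available.

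So the patient can enter, and no rule in the available documents removes or flags that patient.

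**2. How likely is at least one such patient?** Let p be the share of patients with an acute respiratory infection at or just before V1 (assumed). P(at least one of 20) = 1 − (1 − p)^20.

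| p | at least one | at least two |
|---|---|---|
| 2% | 33% | 6% |
| 5% | 64% | 26% |
| 10% | 88% | 61% |
| 20% | 99% | 93% |

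**3. What would it do to SNOT-22?** Let k1 patients carry d1 excess points at V1 that are gone by V2, and k2 patients carry d2 excess points at V2 that were absent at V1. With 20 complete pairs:

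apparent improvement in the mean = (k1·d1 − k2·d2)/20

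- k1 = 1, d1 = 10, k2 = 0: 10/20 = 0.5 points
- k1 = 3, d1 = 20, k2 = 0: 60/20 = 3.0 points
- k1 = 4, d1 = 30, k2 = 0: 120/20 = 6.0 points
- k1 = k2 and d1 = d2: 0
- k1 = 1, k2 = 3, d1 = d2 = 20: (20 − 60)/20 = −2.0 points, an apparent worsening

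The range 0.5 to 6 points therefore applies only if k2 = 0.

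**4. What would it do to a paired test?** This is a simulation of a two-sided signed-rank test at 0.05: n = 20, normal changes, no device effect, k1 patients shifted by 1 or 2 SD of the change, k2 = 0, 4,000 runs per setting. The signed-rank test was chosen for illustration; protocol section 9 names Kruskal-Wallis and rank-sum tests for bacterial load and alpha diversity.

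| k1 | rejection, 1 SD | rejection, 2 SD |
|---|---|---|
| 0 | 3.9% | 4.5% |
| 2 | 6.2% | 7.8% |
| 4 | 10.1% | 16.8% |

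The two figures for k1 = 0 differ only by simulation error.

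**5. Primary endpoint.** Each affected patient is one pair in 20, or 5% of the pairs, in which one swab may show a disturbed community. The documents give nothing from which to size the effect on load or diversity.

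**The case against.** Several stronger readings are tempting and do not survive the text.

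- A reader might infer that COVID-19 forces withdrawal. The list is headed by a permissive *may*, and the sentence says the diagnosis will justify withdrawal. A diagnosis made at V1 after consent might also count as being during the study, so COVID-19 at V1 is not clearly admitted. COVID-19 shortly before V1, and every other infection, remain uncovered.
- A reader might infer that infections that look like benefit stay in while infections that look like harm are removed. For infections other than COVID-19 the plan is symmetric: they are neither excluded at V1 nor named for withdrawal later. For COVID-19, available data are retained, SAP 6.3.3 keeps dropouts in the analysis, and one post-baseline SNOT-22 is enough for the FAS. The documents do not say whether the premature visit includes SNOT-22 or a swab, so loss of these data is possible but not shown.
- A reader might infer a known bias in favour of the device. Its sign depends on infections at both visits, and no rate or effect is given.

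It is also fair to say that V1 records medical history and a rhinologic examination, and that a new infection before V2 should be reported as an adverse event. This helps with later infections. For one already present at V1 it is weaker: section 16.2 appears to exempt pre-existing conditions other than CRS from event reporting, and no prompted question asks about infection. The SAP baseline mock table has a row for symptoms of less than 12 weeks, but no planned analysis uses it.

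Finally, the study is exploratory, SNOT-22 is secondary and descriptive, and p-values are for information only (SAP 6.3.1). The deeper weakness is the absence of a control group. This limits the weight of the point but does not remove it.

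**Conclusion.** The gap stands. Sections 8.3.1.2 and 8.3.2.1 do not agree with each other, and an infection that the protocol itself regards as disturbing the measured community is not screened for at baseline. In an uncontrolled before/after study of 20 pairs, recovery from it cannot be separated from change on the device.

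The size is not known. The 0.5 to 6 SNOT-22 points rest on assumed values (1 to 4 patients, 10 to 30 points) and on no infections before V2; with infections at both visits the net shift can be zero or reversed. The documents support neither a claim that the results are biased in favour of the device nor a claim that COVID-19 cases drop out of the analysis. This is a cheap improvement to design and reporting, not a flaw that invalidates the study.

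**What to change.** 1. Reconcile 8.3.1.2 (and the synopsis list) with 8.3.2.1, so that the COVID-19 sentence refers to a criterion that exists or stands as a separate reason. State whether SNOT-22 and the swab are collected at the premature visit.
2. Add a non-inclusion criterion to 8.3.1.2: acute upper respiratory infection, including COVID-19, at V1 or in the preceding month (the look-back of criterion 1). Allow re-screening once the window has passed.
3. Ask the same prompted infection question at V1 and V2, with the same look-back, and record the answer in the CRF.
4. In the SAP and in the separate microbiome analysis document, pre-specify that the primary microbiome change and the SNOT-22 change are reported with and without patients who had an infection before either visit. The criterion alone would remove infections only at V1 and tilt the comparison against the device; this report keeps the handling symmetric.

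**Cost.** One criterion line, one question asked twice and one extra set of summaries, with no added test or visit. A few inclusions are delayed by some weeks. If 5%, 10% or 20% of candidates were turned away and none returned, reaching 20 would take 20/0.95, 20/0.90 or 20/0.80, that is 22, 23 or 25 candidates; re-screening lowers this. A cold must be distinguished from CRS blockage and discharge by history, so some misclassification will remain. SAP section 12 indicates that data review has already taken place. If enrolment is closed, only item 4 can still be done for this study, using recorded history and adverse events, and its limits should be stated.

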8.3.2.2 Subjects lost to follow-up

If a patient cannot be contacted to collect data at the end of the treatment period after repeated unsuccessful attempts including sending through a registered letter, he/she will be considered "lost to follow-up". But before declaring that a patient is "lost to follow-up", the investigator (or his/her team) must do his/her best effort to contact the patient and attempts should be made via all available routes. A registered letter should be sent to the permanent address on file.

The methods used to attempt to contact the patient should be noted in the patient medical file.

8.3.2.3 Subject replacement

No subject replacement is planned.

8.3.3 Point of enrolment

The subjects will be recruited by the site among outpatients coming for routine consultation because of CRS.

In order to facilitate the enrolment, a study nurse or a CRA will contact patients before the consultation in order to explain the study aim and design. This will allow the patient to have a period for thought before the consultation with the investigator.

When coming for the consultation, the patient will be informed again about the study by the investigator. All questions relative to the study will be answered by the investigator. If the patient agrees to study participation, he/she will sign/date the Informed Consent Form before any study procedure.

8.3.4 Total expected duration of the clinical investigation

The total study duration is planned to be 5 months.

8.3.5 Expected duration of each subject's participation

The duration of each patient's participation is 30 days.

8.3.6 Number of subjects required to be included in the clinical investigation

An arbitrary sample of 20 patients completing the investigation without major protocol deviation has been chosen.

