	
Visit 1 (V1) – (Day 1): Screening/Inclusion Information and consent, demographic data and medical history, ongoing medication, rhinologic examination, inclusion/non-inclusion criteria, collection of middle meatus swab specimens, SNOT-22, reporting of adverse events, dispensation of Healsea® Chronic Nasal Spray.
 
Telephone call 1 (TC1) – (Day 15±3) Investigator/nurse telephone call to review patient status and study progress, adverse events/incidents/expected undesirable side effects and concomitant treatments.
 
Visit 2 (V2) – (Day 30±5): end of treatment End of Healsea® Chronic nasal spray treatment, physical and clinical examination, reporting of adverse events/incidents/expected side effects, collection of middle meatus swab specimens, SNOT-22, subject's satisfaction questionnaire.

Number of Subjects:	An arbitrary sample of 20 subjects
Target Population:	Adults with chronic rhinosinusitis according to EPOS criteria [1].
Permitted and prohibited concomitant medication	
Permitted concomitant medication: Nasal corticosteroids
 
Not permitted concomitant medication: Other nasal irrigations Need for systemic corticosteroids Need for nasal application of antibiotics and systemic antibiotics

Inclusion/Non inclusion criteria:	
Inclusion criteria In order to be eligible to participate in this study, an individual must meet all of the following criteria:
 
 1. Male or female, aged 18 – 70 years 2. Provision of signed and dated informed consent form 3. Stated willingness to comply with all study procedures and availability for the duration of the study 4. Diagnosed with CRS based on the diagnostic criteria of the EPOS guideline 5. Registered with a social security scheme or covered by such a regime 
Non inclusion criteria An individual who meets any of the following criteria will be excluded from participation in this study:
 
 1. Antibiotics or oral corticosteroids intake in the month prior to the study 2. Endoscopic sinus surgery in the past 6 months 3. Cystic fibrosis 4. Wegener's granulomatosis 5. Immunodeficiency

	
 6. Defective access to middle meatus 7. Lidocaine allergy 8. Known hypersensitivity/allergy to any component of the test device 9. Pregnant/Lactating female or absence of efficient contraception 10. Under tutorship or guardianship
Number of sites:	1

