8.3.7 Estimated time needed for the enrolment

It is expected to enrol 20 patients within 4 months.

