4. SAMPLE SIZE

An arbitrary sample of 20 subjects completing the investigation without major protocol deviation has been chosen.

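### The stated sample size is 20 patients completing without major deviation, but the plan enrols an expected 20, replaces none and allows for no losses

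*Protocol*

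**What the plan says.** Protocol 8.3.6 carries the heading "Number of subjects required to be included in the clinical investigation". The text beneath it reads "An arbitrary sample of 20 patients completing the investigation without major protocol deviation has been chosen". SAP section 4 has the same sentence with one word changed: "An arbitrary sample of 20 subjects completing the investigation without major protocol deviation has been chosen".

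The figures for inclusion are these:

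- The synopsis gives "An arbitrary sample of 20 subjects", with no condition on completion or deviations.
- Protocol 8.3.7 says "It is expected to enrol 20 patients within 4 months".

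Replacement is excluded twice: "No replacement of subjects is planned" (Protocol 8.1.7) and "No subject replacement is planned" (Protocol 8.3.2.3).

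The protocol also describes how patients may be lost. Section 8.3.2.1 covers withdrawal by the patient or the investigator and adds that "the diagnosis of COVID-19 during the study will justify the withdrawal of the patient from the study". Section 8.3.2.2 covers loss to follow-up. Section 13 lists four kinds of major deviation: eligibility, compliance with treatment, swab collection and forbidden medication. Neither document gives an expected rate for any of these.

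**The concern.** The number to include and the number evaluable are different quantities, and here both are 20. They can be equal only if nobody withdraws, nobody is lost to follow-up and nobody has a major deviation. With replacement ruled out and no margin in enrolment, the plan has no means of making good a single loss.

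What is at stake is how the study will be read. The stated sample size is the figure against which disposition and completeness are judged. One ordinary dropout would make the study appear to have missed its target. A reader of the synopsis and a reader of 8.3.6 would also come away with different ideas of what the 20 counts.

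**Working it through.** **Inputs from the documents.** Target completing without major deviation: 20 (Protocol 8.3.6, SAP 4). Expected enrolment: 20 (Protocol 8.3.7, and the synopsis without qualifier). Replacement: none (Protocol 8.1.7, 8.3.2.3). Loss rate: not given. Effect size: declared not applicable because the study is exploratory (Protocol 7.4).

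**The plan's own figure.** The 20 is declared arbitrary, and there is no effect size, standard deviation or power from which to rebuild it. The only check available is whether enrolment and target agree. They do at zero loss: 20 × (1 − 0) = 20.

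**Assumptions.** Let p be the combined probability that an enrolled patient withdraws, is lost to follow-up or has a major deviation. All values of p are assumed, and losses are taken as independent between patients.

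**Formulas, with 20 enrolled.** Expected number evaluable = 20(1 − p). Probability that all 20 are evaluable = (1 − p)^20.

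| Assumed p | Expected evaluable | Probability that all 20 are evaluable |
|---|---|---|
| 1% | 19.8 | 0.99^20 = 0.818 |
| 2% | 19.6 | 0.98^20 = 0.668 |
| 5% | 19 | 0.95^20 = 0.358 |
| 10% | 18 | 0.90^20 = 0.122 |
| 15% | 17 | 0.85^20 = 0.039 |

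The probability equals one half when p = 1 − 0.5^(1/20) = 0.034. Above a loss rate of about 3.4%, missing the target is more likely than meeting it.

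**The reverse calculation.** If 20 evaluable patients were really required, the enrolment giving an expected 20 is 20/(1 − p), rounded up: 20/0.95 = 21.1, so 22; 20/0.90 = 22.2, so 23; 20/0.85 = 23.5, so 24. No figure above 20 appears in either document.

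**Where the shortfall lands.** The analysis set closest to the target is the Per Protocol Set (SAP 5). It is counted in the disposition table, but no efficacy table listed in SAP 13.2 is run on it. The secondary efficacy analyses use the FAS, which keeps patients with major deviations who have a post-baseline SNOT-22, unless the data review excludes them. Available data from withdrawn patients are retained (Protocol 8.3.2.1, SAP 6.3.3). The population for the primary microbiome analysis is left to the sequencing results (SAP 10.1). A patient without a swab at V2 gives no before-and-after pair, so the number of pairs may also fall below 20.

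**The case against.** The strongest reply is that Protocol 8.3.7 estimates recruitment time and is a forecast, not a cap. No passage sets a maximum enrolment, so 8.3.6 could be read as an instruction to go on including patients until 20 have completed without major deviation. On that reading zero loss is not needed, and the fault is only that the number to include is not stated separately. It is also fair to say that an arbitrary number in an exploratory study is not a hard threshold, that the loss rates above are assumed, and that no analysis specified in these documents depends on the 20.

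The points about consequence stand, and they keep this a minor finding. The alternative reading does not. Including further patients to make up for those lost is replacement in substance, and the protocol excludes replacement in two places. Nothing provides for enrolling more than 20. Even if 20 evaluable were the true target, the number to include, which the heading of 8.3.6 announces, would still be missing, and the synopsis and 8.3.7 would mislead.

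**Conclusion.** The concern holds. Protocol 8.3.6 and SAP 4 state a sample size that the plan's own enrolment and replacement rules do not deliver unless there are no losses at all. At an assumed 5% to 15% loss the expected shortfall is 1 to 3 patients. That range is illustrative, but the conclusion does not need a pessimistic rate: even at 2% there is about a one-in-three chance (1 − 0.668 = 0.332) of falling short.

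The effect on the results is small. No power claim is lost, the SAP offers p-values for information only (section 6.3.1), and the shortfall falls on a set with no listed efficacy table. The text should be corrected, but the design and the analyses are not put in doubt.

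**What to change.** Restate Protocol 8.3.6 and SAP 4 so that they agree with the synopsis, the two no-replacement statements and 8.3.7. For example: 20 patients will be included, without replacement; the number completing without major protocol deviation may be lower. If an expected evaluable number is given, label it as resting on an assumed loss rate, such as 19, 18 or 17 at 5%, 10% or 15%.

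If the sponsor did intend 20 evaluable patients, the alternative is to state a separate, larger enrolment figure with its assumed loss rate and to amend the synopsis and 8.3.7 to match.

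The first option costs one sentence in each document and needs no extra patients, data or analyses. Its drawback is that the evaluable number looks slightly less favourable. SAP section 12 already records a change made after data review, so any change to the SAP wording should be dated and recorded there as a clarification, so that it is not taken for a target lowered in the light of the data.
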